Recently, data have emerged suggesting that computational modelling of a patient's heart based on 3D MRI reconstructions can enable prediction of optimal targets for VT ablation non-invasively. This has been confirmed in both retrospective and prospective studies.⁸ This involves high resolution MRI imaging with late-gadolinium enhancement (LGE) to assess the three-dimensional geometry of the scar, followed by reconstruction of the patient's heart *in silico*^{9,10}. Fibre orientation is established and overlaid onto this model¹¹. Standard electrophysiological properties are applied to the different categories of tissue as defined by the LGE signal intensity, namely, normal tissue, scar and grey zone. Using computational modelling, this "virtual heart" is then analysed for different potential ventricular tachycardia circuits that are theoretically sustainable based on the information supplied. A virtual electrophysiology study with programmed stimulation is conducted by virtually pacing the heart model from various different locations⁹. An algorithm is used to predict optimal ablation sites to terminate all possible VT circuits in this model heart. The algorithm initially generates "primary sites", which are the initial locations which have the potential to sustain ventricular tachycardia in the patient's heart. The model then undergoes virtual VT ablation of these primary sites and the prediction algorithm is re-run. This may generate a new VT-sustaining substrate and give predictions of "secondary sites" which can sustain VT in the post-ablation heart. The process is repeated until the heart is no longer VT-inducible.¹². In this way, not only should the patient's clinical VT be ablated, but all future potential ventricular tachycardias supportable by the substrate in its current form should also be avoided, reducing the need for repeat VT ablation.

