2 RATIONALE

Current invasive substrate mapping techniques are time and labour intensive. The ability to identify arrhythmogenic from non-arrhythmogenic areas within the same scar is limited, leading to prolonged procedure time and the potential overuse of ablative energy. Activation mapping during ventricular tachycardia, the gold standard for defining the critical isthmus sustaining the arrhythmia, is significantly limited by hemodynamic instability.

Image-guided VT ablation has been shown to improve substrate definition and may underpin improved outcomes in certain patient populations^{13,14}. Given the newly emerging field of personalised medicine and computation modelling this study will help to assess if an MRI-based, computer generated model accurately correlates to the invasive findings from an EP study with regards to targeting ablation in VT. If the model proves to be accurate, this will help to advance the process of *in silico* planning of VT ablation and potentially lead to improvements in outcomes of VT ablation, as well as reducing the need for repeated procedures. Results from the invasive studies can also be fed back into the computational model in an attempt to improve its accuracy. Furthermore, by assessing the electrophysiological properties of the computer generated predicted sites, we may learn which signals may indicate a critically important part of the VT circuit which traditional electroanatomical maps may miss.

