4.1 Objectives

- To perform high resolution cardiac MRI prior to undergoing catheter-based VT ablation in order to non-invasively assess scar and provide data for computational modelling and prediction of likely VT circuits *in silico*.
- To assess the accuracy of the *in silico* predicted sites when compared to invasively obtained electrophysiological data.
- To assess the ventricular scar characteristics in patients with scar-dependent VT using high-definition invasive mapping.
- To invasively assess the *in silico* predicted sites in order to ascertain the electrophysiological properties which likely lead to their prediction as key sites for arrhythmogenesis.
- To corroborate the *in silico* predictions with the invasive findings during catheter-based VT ablation.

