4.2 Outcome

- Assessment of the degree of validation of *in silico* computational modelling by invasive ventricular scar interrogation to see if the predicted sites match those sites which would have been determined as important from invasive mapping.
- Qualification of the electrophysiological characteristics of those sites which the computational model predicted in an attempt to see what it is about them that makes them likely to be key to maintaining the arrhythmia. With our mapping techniques, we can assess not only the amplitude and morphology

of the electrograms from these areas, but also the directionality of wavefronts to see if this is an important feature. With the additional benefit of the 3D computational model, we may be able to gain some insight into the 3D nature of channels which form part of the VT substrate.

- Assessment of the change in the invasive electrophysiological characteristics of distant sites following ablation of the primary predicted *in silico* sites. By ablating the predicted areas, it is possible that when we re-map distant points, they may be a change in their electrophysiological properties. There may be a change in variables such as the stim-QRS latency, the QRS morphology, the capture threshold and the nature of the exit site (e.g. multiple-exit site changing to single-exit site).
- Assessment of the frequency of ventricular arrhythmia, frequency of therapy delivered from an ICD (if applicable) and duration until first delivered therapy on serial heart rhythm monitors. Also assessment of patient's symptoms and adverse effects on clinical consultation.

5 STUDY DESIGN and METHODS of DATA COLLECTION AND DATA ANALYSIS

The study will be a single centre, prospective study based at St George's University Hospitals NHS Foundation Trust in London. Consecutive patients presenting to the hospital with an appropriate scar-dependent, sustained monomorphic ventricular tachycardia, requiring catheter ablation, will be screened for inclusion into the study. Full inclusion and exclusion criteria are listed below. Patients are likely to be predominantly outpatients, requiring elective VT ablation, however inpatients may also be included in the study.

If found eligible for the study, the patient will be approached by one of the study investigators and a Patient Information Sheet (PIS) will be offered. Written consent will be obtained if the patient is willing to proceed.

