If included in the study, de-identified, anonymized MRI images from patient's routine scan will be transferred to Johns Hopkins University, Baltimore Maryland, for computational analysis. The patient's MRI images will be reconstructed, analysed and a 3D geometric model of the patient's heart formed. From this, a computer-generated model of the patient's heart will be created. As described above, a virtual EP study, VT ablation and generation of both primary and secondary sites will be generated. The computation model as well as the locations of these primary and secondary sites will again be stored securely and transferred back to the primary research centre.

The patient will then undergo traditional endocardial, and in appropriate cases, epicardial, mapping and ablation of ventricular tachycardia, using the techniques previously described ^{1-3,7,15}. Patient preparation on the day of the procedure will be as for any other clinical VT ablation. Ablation technique will depend on whether or not there is a documented 12 lead ECG of the patient's clinical VT and also whether or not the VT is haemodynamically tolerated (stable) or not (unstable). This will be decided by the operator and will follow usual practice for VT ablation.

We will use a multipolar mapping catheter, in order to create a high-density map and gain as detailed information as possible about the substrate. Multipolar catheters are used as standard of care for VT mapping and ablation in our institution and most other high-volume specialised centres. The 3D computational model will be merged with the traditional 3D electroanatomical map generated during the VT ablation. Particular care will be taken when mapping the points of interest from the computational prediction to assess their particular electrophysiological properties. This will allow us to assess variables such as wavefront directionality, amplitude and morphology to see if they have a particular signal which marks them as important in sustaining the VT circuit and therefore conferring their importance in predicting potential sites for ablation. By overlaying the computer generated model onto the invasive map, we will be able to corroborate the predicted model's findings with traditional mapping techniques.

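### Agreement with invasive mapping has no benchmark from the MRI scar map, so it can show how accurate the whole pipeline is but not what the simulation contributes

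*Combined protocol and SAP*

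**What the plan says.** Section 1 describes the model in two steps. Electrophysiological properties are assigned to "different categories of tissue as defined by the LGE signal intensity, namely, normal tissue, scar and grey zone", and circuits are then simulated on the resulting heart.

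The accuracy outcome has one comparator throughout:

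- Section 4.1 sets the "predicted sites when compared to invasively obtained electrophysiological data".
- The first outcome in section 4.2 asks whether the "predicted sites match those sites which would have been determined as important from invasive mapping". It calls this validation of the computational modelling, obtained by invasive interrogation of ventricular scar.
- Section 5 overlays the model on the invasive map, so that "we will be able to corroborate the predicted model's findings with traditional mapping techniques".

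Section 7.1.1 restricts entry to scar-dependent VT. Section 7.2.1 says that a minimum of 20 patients will be enough to judge whether the computational modelling is accurate. Grey zone is mentioned only in section 1, as a model input. Nowhere is the scar or grey-zone map, or any set of sites taken from it, scored against the invasive reference.

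**The concern.** Both sides of the comparison are drawn towards scar for reasons unrelated to the simulation. The model's sites come from circuits simulated on the segmented scar. The invasive targets come from scar interrogation in patients selected because scar causes their arrhythmia. A rule that placed sites in the segmented scar with no simulation could also earn some agreement.

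Sections 4.2 and 7.2.1 credit agreement to the computational modelling, and section 2 says that an accurate model would advance in silico planning. If much of the agreement came from the scan, a simulation that added little could still be reported as validated. The trial would not show whether the computation is needed. A benchmark of random sites over the whole ventricle would not help, because it leaves the scar-driven agreement in place.

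**Working it through.** **The plan's own figure.** The sample size of 20 comes with no alpha, power, expected agreement or precision target. It cannot be reproduced, and it is not called wrong here.

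**What the documents establish.** The comparator is invasive mapping only (4.1, 4.2, 5). The model input is the LGE segmentation (1). The reference comes from scar interrogation in scar-dependent VT (4.2, 7.1.1). The omission and the shared location follow from the text. The size of the effect does not. Every number below except n = 20 is assumed.

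**1. Match rate without simulation, by area.** Assume a matching area of 5 to 10 cm² lying wholly in the grey zone, a grey zone of 20 to 40 cm², and a ventricular surface of 150 to 200 cm².

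- Random site in grey zone: 5/40 = 12.5% to 10/20 = 50%.
- Random site anywhere: 5/200 = 2.5% to 10/150 = 6.7%.

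**2. Relaxing the assumption that the whole target lies in grey zone.** Let t be the share of the surface that is invasively important, f the share that is grey zone, and s the share of the important area inside grey zone. A random grey-zone site matches at rate t × s/f and a random ventricular site at rate t, so the enrichment is s/f.

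- For f = 0.10 to 0.30 and s = 0.60 to 0.90, enrichment runs from 0.60/0.30 = 2.0 to 0.90/0.10 = 9.0.
- Example: t = 0.10, f = 0.20, s = 0.90 gives 0.10 × 0.90/0.20 = 45%, against 10%.
- If s equals f, the enrichment is 1 and the scan alone contributes nothing. The documents do not say where between these cases the trial lies.

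**3. Effect on a conclusion from 20 patients.** The protocol plans no such test; this only shows what the choice of benchmark does. Take one match or no-match per patient and an exact binomial rule with one-sided alpha of at most 0.025.

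| Benchmark | Rule | Alpha | True match rate | Probability of passing |
|---|---|---|---|---|
| 10% (whole ventricle) | ≥ 6/20 | 0.011 | 45% (no simulation) | 0.94 |
| 45% (grey zone) | ≥ 14/20 | 0.021 | 45% (no simulation) | 0.021 |
| 45% (grey zone) | ≥ 14/20 | 0.021 | 70% | 0.61 |
| 45% (grey zone) | ≥ 14/20 | 0.021 | 80% | 0.91 |

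**4. Precision of a paired difference at n = 20.** The 95% half-width is 2.093 × SD/√20. The last column is the difference detectable with 80% power by a two-sided paired t-test at 5%.

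| SD of per-patient difference | Half-width | Detectable difference |
|---|---|---|
| 0.2 | 0.094 | 0.132 |
| 0.3 | 0.140 | 0.198 |
| 0.4 | 0.187 | 0.264 |

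If each patient gives a single match or no-match near 50% against a fixed benchmark, the SD is √(0.5 × 0.5) = 0.5 and the half-width is 2.093 × 0.5/√20 = 0.234. For scale, 14/20 = 70% has an exact 95% CI of 46% to 88%.

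**The case against.** The strongest reply is that the first aim in section 4 concerns the accuracy of an MRI-based model as a whole. Accuracy against a reference standard is a complete question, and no aim claims that simulation improves on segmentation. This stands. It is why the added comparison should sit beside agreement with invasive mapping and not replace it. It does not remove the problem of attribution, because sections 4.2 and 7.2.1 name the computational modelling as the thing validated.

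Two sentences in section 2 invite a stronger reading than they bear. "Image-guided VT ablation has been shown to improve substrate definition and may underpin improved outcomes in certain patient populations" concerns imaging used within an ablation procedure, in some populations. It does not concede that a scan alone locates the targets. "The ability to identify arrhythmogenic from non-arrhythmogenic areas within the same scar is limited" follows a sentence about current invasive mapping and describes a limit of that technique. It does not describe a gap between segmentation and simulation. Since invasive mapping is also the reference here, the limit cuts the other way: a reference that separates areas within scar poorly would let random scar sites match too, and could shrink a real difference.

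A third objection is unequal verification. Section 5 promises particular attention to mapping the model's points of interest, and section 8.1 counts extra mapping of the predicted targets in the added procedure time. Random scar sites would receive no such attention, so a positive difference could reflect mapping effort. This stands, and the fix must deal with it.

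Finally, the magnitude rests wholly on assumed areas and SDs, and section 1 does not say that predicted sites must lie in grey zone. Both points are right. They leave the size unknown, which is a reason to measure it.

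**Conclusion.** The point holds as a limit on attribution. The planned comparison can estimate how often the pipeline agrees with invasive mapping. It cannot show how much of that agreement the simulation provides, because no benchmark from the same scan is scored. On the assumed inputs, the scan alone could raise the match rate 2- to 9-fold over random ventricular sites. The documents supply none of these inputs, and the true enrichment could be smaller.

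A reader might infer that the accuracy outcome is invalid, or that the simulation adds nothing. The documents support neither. Nor do they support making the increment over the scan the main result. Adding the benchmark is a cheap improvement, and with 20 patients it can show only a large difference with any confidence.

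**What to change.** Keep agreement with invasive mapping as the main result and add a pre-specified companion analysis to section 4.2:

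1. **Match rule.** Fix it in advance and apply it identically to both sets of sites. Sections 4.2 and 5 do not yet define one, and the main result needs it as well.
2. **Benchmark.** For each patient, draw the same number (or area) of sites at random within the MRI scar/grey-zone segmentation. Repeat the draw many times and average the agreement.
3. **Reference.** Define the invasively important sites from the standard map, leaving out points taken because the model flagged a location. Both sets are then scored against equal mapping effort. Such points need to be tagged in the data when acquired.
4. **Estimate.** Report the within-patient difference, model minus segmentation benchmark, with a 95% CI and the patient as the unit.
5. **Interpretation.** Attribute agreement to the simulation only if the interval lies above zero. If it includes zero, report that added value over the scan was not shown. Do not report that it is absent, given the small sample and the imperfect reference.
6. **Data.** Ask for the segmentation to be returned with the model. Section 5 lists only the model and the site locations.

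The cost is protocol wording, some offline analysis and one extra export. It needs no extra patients, scans or procedure time, and no change to the ablation. The drawbacks are an imprecise difference and a headline that may look less favourable than raw agreement.

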Ablation technique will be as per standard of care and the order of ablation will be guided by standard invasive mapping. However if we ablate at an area which the MRI-model also predicted to be important, we will re-map the surrounding myocardium to see if there has been an effect of the electrophysiological properties of these distant sites following ablation of the predicted sites.. The computer model will not alter the extent of ablation and will not lead to ablation of any areas which wouldn't otherwise be ablated using traditional mapping.

The patients will be followed up as standard of care at 3, 6 and 12 months following their procedure with ICD interrogation, or in the case of absence of an ICD an extended ECG monitoring period. We will use this to assess frequency and duration of recorded arrhythmias time to recurrence of ventricular arrhythmia as well as frequency of therapy delivered by the device. We will also use data from their clinical consultation to evaluate their symptoms and response to the procedure including any adverse events.

STUDY FLOW CHART

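### In the readable text, the invasively important sites are not fixed before the model's predictions can be seen, and extra mapping goes to predicted sites, so the agreement outcome is open to review bias and unequal search effort of unknown size and direction

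*Combined protocol and SAP*

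**What the plan says.** Section 4.2 puts agreement first among the outcomes: the invasive study is done "to see if the predicted sites match those sites which would have been determined as important from invasive mapping". The second outcome describes the electrograms at predicted sites. The third concerns changes at distant sites after predicted sites are ablated.

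Section 5 gives the steps. After modelling, "the locations of these primary and secondary sites will again be stored securely and transferred back to the primary research centre"; the next paragraph has the patient then undergo conventional mapping and ablation. A multipolar catheter is used to build a high-density map of the substrate. "The 3D computational model will be merged with the traditional 3D electroanatomical map generated during the VT ablation". On the predicted points it adds: "Particular care will be taken when mapping the points of interest from the computational prediction to assess their particular electrophysiological properties". The same paragraph says that the overlay will serve to corroborate the model's findings. On re-mapping: "However if we ablate at an area which the MRI-model also predicted to be important, we will re-map the surrounding myocardium".

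Section 6 requires, for emergency admissions, that there be time to finish the computation before ablation. Section 8.1 attributes the lengthening of the procedure to co-registration, additional mapping of predicted targets and re-mapping after predicted sites are ablated.

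On safeguards, Section 5 states "The computer model will not alter the extent of ablation and will not lead to ablation of any areas" that standard mapping would have spared. Sections 8 and 8.1 repeat that the model does not determine what is ablated.

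**The concern.** An agreement study needs a reference that does not depend on the test under assessment. The conditional wording of the first outcome shows that this is intended, but the readable text contains no step that secures it.

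Two mechanisms are open:

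- **Review bias.** A borderline electrogram may be judged differently by someone who knows that the model marked that spot.
- **Unequal search effort.** Where more points are taken, more can be found, and more can also be ruled out.

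If either operates, the agreement result cannot separate a model that located the important sites from a procedure that looked harder, or judged differently, where the model pointed. Section 7.2.1 justifies the sample of at least 20 patients by its ability to show whether the model is accurate, so this affects the main result. More patients would narrow the interval around the estimate without removing the bias. Mapping density also cannot be equalised once a procedure is over, so the order has to be settled before data are collected.

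**Working it through.** No stated figure can be reproduced here. The plan gives no expected agreement, accuracy target or matching rule. The check sets the passages side by side.

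**1. When are the predictions available?** Before the procedure. Section 5 returns the site locations to the centre and then describes the procedure. Section 6 says the same explicitly for emergency admissions.

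**2. Are they used during the procedure?** Yes. Section 8.1 counts co-registration and additional mapping of predicted targets as procedure time. The re-mapping rule in Section 5 works only if someone in the team knows, when a site is ablated, that it was predicted.

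**3. Is mapping effort equal?** Not entirely. Every patient has a high-density map, which is the common baseline. On top of it, the additional mapping named in Section 8.1 goes to predicted targets, and nothing comparable is described at non-predicted scar. Section 8.1 is the stronger evidence here, because the sentence on particular care in Section 5 is written for the second outcome. Re-mapping reaches surrounding and distant myocardium, but it is triggered only by predicted sites and serves the third outcome.

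**4. Does any step separate the reference from the predictions?** The candidates are:

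- *Map, then merge (Section 5).* This suggests that a map exists before the overlay. It does not say that important sites have been marked by then, or that the operator has not yet seen the site list.
- *No effect on order, extent or set of ablation (Sections 5, 8 and 8.1).* These statements cover treatment. They do not say when a site is labelled important, or how densely each area is mapped.
- *Areas deemed important are ablated whether or not the model predicted them (Section 8.1).* This links importance to ablation, but no section defines one by the other.
- *Recording, locking, blinded or independent reading, or exclusion of the additional points from the comparison.* None appears in the readable text.

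**5. Which way would bias run?** Either way. Knowing the predictions, or searching harder at predicted sites, could add matches. Denser mapping there could also show that an apparent match is false and remove it. To put a size on the net effect one would need the agreement against a locked reference and the share of labels changed in each direction. The documents give none of these, and any figure would reflect only the values assumed, so no numerical illustration is offered.

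**The case against.** The case on the other side is substantial.

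- **The order may already be specified.** The study flow chart in Section 5 is where one would look for it, and it is not readable. This stands: the claim is limited to the readable text.
- **Every patient has a dense baseline map.** This stands as mitigation. It narrows the difference in effort, but the additional mapping still goes to predicted targets.
- **Prior viewing by the operator is inferred.** Section 6 returns the output to the investigators for analysis, and Section 5 reads most naturally as map first, overlay second. This stands in part: no sentence says that the operator sees the predictions early. None says the operator does not, and Section 7.3.1 describes the research team as belonging also to the clinical team.
- **The sentence on particular care belongs to the second outcome.** Correct, and that mapping is needed. The difficulty is that one overlaid map also serves to corroborate the model, with nothing keeping the two uses apart.
- **If important simply means ablated, the plan already declares the reference independent.** That would help, but the plan does not define it so and describes no step that enforces it.
- **Neither an important site nor a match is defined, which is a larger gap.** True, and locking does not close it. Locking fixes when the judgement is made, which a later definition cannot supply.

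A reader might infer that reported agreement will be inflated, that the operator will work from the predictions, or that the model will steer treatment. The documents support none of these: the direction is undetermined, viewing before labelling is not stated, and the text says that ablation is unaffected.

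**Conclusion.** The point holds as a cheap improvement. The plan returns the predictions before the procedure, directs additional mapping to predicted targets within it and corroborates the model on the overlaid map, yet the readable text neither fixes the important sites beforehand nor keeps the additional points out of the agreement comparison. The first outcome is therefore open to review bias and unequal search effort, reduced but not removed by the baseline map, the map-then-merge wording and the statements on ablation.

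Size and direction cannot be determined from the documents. The conclusion assumes that the unreadable flow chart does not already set the order; if it does, what remains is to repeat the order in the text and to say which points enter which analysis.

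**What to change.** Add to Section 5:

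1. The operator records, time-stamps and locks the sites judged important on the standard invasive map before the model or site list is shown or overlaid. An existing team member who is not operating holds the predictions until then.
2. Agreement for primary predicted sites is computed only from the locked sites and pre-overlay points. Additional points at predicted sites serve the electrogram-characteristics outcome, and re-mapping points serve the distant-site outcome.
3. Three groups are reported separately and labelled as not blinded: secondary predicted sites, which Section 1 describes as those "which can sustain VT in the post-ablation heart"; important sites found after the lock; and any case in which the predictions were seen before the lock.

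The overlay, additional mapping and re-mapping then follow as planned. Mapping and ablation technique and extent are unchanged. On ablation technique Section 5 says "This will be decided by the operator and will follow usual practice for VT ablation", and the lock only records the operator's judgement. If the flow chart already gives this order, state it in the text and add items 2 and 3.

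The cost is protocol wording, a time-stamped save and a custodian role for an existing team member, with no extra reader, visit or procedure. The downsides are a short marking step that must fit within the stated 10% limit on added procedure time (roughly 30 minutes in Section 8), a slightly later overlay, and possibly a lower reported agreement. The documents do not show whether a non-operating team member is available at every procedure, so the centre should confirm this.
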